Sample size	A target sample of 100 patients was chosen based on funding constraints, power / sample size considerations, and expected loss to follow-up of 20-30%. The minimum number of trial completers required to have 80% power to detect an HbA1c difference of 0.5% is 80.
Follow-up	Follow-up (week 5-6) CDE virtual education and feed-back session. 12-week bloodwork encounter at outpatient lab. 12-week in-person study encounter to complete study measurements. After conclusion of the 12 week trial period: Post-trial qualitative interviews with select consenting participants. Post-trial administrative linkage to examine outcomes at 24-52 weeks from randomization – no direct participant involvement.

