- *No specific monitoring of glucose* – Participants will be discouraged from accessing FreeStyle Libre 2 glucometers or other CGM during the study period. They will be free to use capillary blood glucose monitoring according to their own interest and motivation, or as directed by the CDE nurse. Advice and handouts will be provided to isCGM participants on recognizing and managing hypoglycemia.
- *Alberta Health Services Diabetes Education Group Classes* – Participants will be referred to Alberta Health Service's standard diabetes education group classes and advised to register according to their interest and motivation.
- *CDE Education and Feedback* – A CDE nurse will assess the participant. The CDE nurse will provide general diabetes education, and individualized recommendations on lifestyle (diet and physical activity) changes to improve glycemic control. Two encounters will take place with the CDE nurse. The first will occur during weeks 1-2, and the second during weeks 5-6. CDE nurses will provide education and advice according to their usual training and practices. CDE encounters will take place either in-person, or virtually, over Zoom.

Study period – The trial period will be 12 weeks. From 12 weeks onwards, select participants will be approached to participate in semi-structured qualitative interviews. Linkage of participant information to Alberta administrative health care data may occur up to 3 years after trial completion to allow examination of diabetes outcomes on an observational basis up to 52 weeks from randomization.

Blinding

- This trial is open-label. Neither patients, investigators, nor statistical analysts will be blinded to treatment allocation.

Post-Trial Observational Follow-Up – Patients will be reviewed on NetCare for laboratory values and health care utilization at 24 and 52 weeks following randomization. NetCare data accrued up to 64 weeks post-randomization will be reviewed to identify nearest lab values for the 52-week time point.

Post-Trial Qualitative Study of Experiences Using isCGM – Consenting patients and providers will be contacted after the 12 week study period to participate in semi-structured interviews exploring their experiences using isCGM or managing their blood glucose without isCGM.

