24-52 Week Post-Trial Observational Follow-up: After the trial ends, we will send out reminder letter to all participants and their providers encouraging them to have routine diabetes assessments, including laboratory measures, done. We will ascertain the effect of the intervention on HbA1c at 24 and 52 weeks, by review of NetCare. NetCare data up to 64 weeks post-randomization may be reviewed to assign the nearest lab value to the 52 week time point.

Other Quantitative Variables Measured:

Case report forms are provided in Appendix 5.

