- *Limited trial period of 12 weeks.* There is the possibility that insufficient time may have elapsed by the 12 week study HbA1c to see the effect of the intervention, since the 12 week HbA1c may be influenced by blood glucose exposure early in the trial period, before isCGM-based changes are made. Additionally, the 12 month outcome will not be able to speak to the sustainability of any isCGM benefits detected. We have designed a post-trial observational follow-up to address the longer term outcomes of episodic isCGM, recognizing that the follow analysis will no longer benefit from the expected confounder balance of randomization, as participants who consent to data linkage and who have HbA1c measurements post-trial will represent a non-random subset of those initially randomized.
- *Limited support to titrate anti-hyperglycemic medications.* The presumptive mechanism for any improvement in glycemic control is improved diet and lifestyle modification in adults randomized to isCGM. An alternative mechanism may be more rapid medication titration based on isCGM data, instead of HbA1c measurements, which are recommended at intervals no less than 90 days. While the

CDE algorithm (currently under development) may have a role for CDE-to-provider suggestions for medication changes, the intervention is not intended to provide further support or practice change related to provider prescribing (e.g.: decision support, alternate prescribers, provider training).

- *Sample size still has a 20% risk of type 2 error* – Our study is powered to detect a 0.5% difference in HbA1c at a power of 80%. The type 2 error rate (failure to detect a difference on such a difference truly exists) is still 20%, though may be slightly lower if loss-to-follow-up is minimized and recruitment approaches the full 100 participants.

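### The rule that picks the HbA1c nearest to week 52 is capped at week 64 but has no lower limit, so a value from around week 24 can be reported as the 52-week result

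*Combined protocol and SAP*

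**What the plan says.** Section 10 sets the post-trial aim: "We will ascertain the effect of the intervention on HbA1c at 24 and 52 weeks, by review of NetCare". It then gives the selection rule: "NetCare data up to 64 weeks post-randomization may be reviewed to assign the nearest lab value to the 52 week time point". Section 6 (Post-Trial Observational Follow-Up) has the same pair of statements: "Patients will be reviewed on NetCare for laboratory values and health care utilization at 24 and 52 weeks following randomization", followed by "NetCare data accrued up to 64 weeks post-randomization will be reviewed to identify nearest lab values for the 52-week time point".

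No study blood draw is scheduled after week 12. Post-trial values come from routine care, prompted by a reminder letter to participants and providers (Section 10).

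The post-trial paragraph of Section 14 names regression models but gives no rule on lab dates. The HbA1c form in Appendix 5.5 covers baseline and 12 weeks only.

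Section 4 lists glycemic control at 24-52 weeks as a secondary objective. Section 17 states its purpose: "We have designed a post-trial observational follow-up to address the longer term outcomes of episodic isCGM".

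**The concern.** The authors foresaw that routine draws would not fall on week 52 and limited how late a value may be. They set no limit on how early it may be, no maximum distance from week 52, no point at which the outcome becomes missing, and no bar on one measurement serving both week 24 and week 52.

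The 52-week result is there to show whether an early difference lasts. If some of the values behind it were really taken around week 24, it is partly a repeat of the 24-week result. The two time points then look more alike than they are, and a reader cannot tell how much of the agreement comes from shared data. Section 6 also says that the analysts are not blinded, which is a further reason to settle the choice of value before the data are seen.

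**Working it through.** **The plan's own figures.** The plan gives no calculation for the post-trial outcome. Its one powered figure, 40 completers per arm for a 0.5% difference with SD 0.78% (Section 14), reproduces: a two-sample t-test at two-sided 5% and 80% power needs 39.19, rounded up to 40 per arm. The sidedness is assumed, because the plan does not state it. This point does not depend on that figure; 0.5% is used below only as a scale.

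**Distances allowed by the rule.**
- Late side: 64 − 52 = 12 weeks at most.
- Early side: no stated limit. A week-24 value is 52 − 24 = 28 weeks early.

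**The rule applied to hypothetical draw dates.** The rule takes the draw at or before week 64 with the smallest |week − 52|. Week 24 is read in the same way, because no other rule is given. Week 12 is the trial draw.

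| Draws at weeks | Used for week 52 | Used for week 24 | Week 52 under a 40-64 window |
|---|---|---|---|
| 12, 24 | 24 | 24 | missing |
| 12, 24, 66 | 24 | 24 | missing |
| 12, 30 | 30 | 30 | missing |
| 12, 24, 63 | 63 | 24 | 63 |
| 12, 26, 39, 52 | 52 | 26 | 52 |

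In the first three rows one measurement serves both time points. The last two rows show that the rule works when a later draw exists.

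**Who is affected.** Any draw in weeks 40-64 is at most 12 weeks from week 52, and any draw before week 40 is more than 12 weeks away. So a value from before week 40 is used only for a participant with no draw in weeks 40-64, a span of 64 − 40 = 24 weeks. For the value to come from week 24 itself, there must be no draw after week 24 up to week 64, a span of 64 − 24 = 40 weeks.

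**Size of the distortion (illustration).** Let p be the share of participants counted at week 52 who have only the early lab. Assume that p is the same in both arms and that the arm difference at each time does not depend on who has only the early lab. Then

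reported difference = p × (difference at week 24) + (1 − p) × (difference at week 52).

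Take 0.5% at week 24 and 0 at week 52:
- p = 0.20: 0.20 × 0.5 + 0.80 × 0 = 0.10%.
- p = 0.40: 0.40 × 0.5 + 0.60 × 0 = 0.20%.

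**Scale.** With SD 0.78% and 40 per arm, the standard error of a difference is 0.78 × √(2/40) = 0.174%. The illustrated bias is therefore 0.10/0.174 ≈ 0.6 to 0.20/0.174 ≈ 1.1 standard errors. The SD is the plan's 3-month value, and the number with post-trial labs is unknown, so this ratio is only a guide.

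**The case against.** The best defence is that the sentences mainly say how far forward to search NetCare. Neither says that a distant value must be accepted or that one value may be used twice. That is fair as to intent. But the text does name a way of assigning a value to week 52, and nothing in it would stop an analyst from taking the week-24 lab.

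A second defence is that the labels imply a floor. The synopsis describes "Post-trial administrative linkage to examine outcomes at 24-52 weeks from randomization", and other sections call the follow-up post-trial. These labels describe a period and are not a selection rule. Even read as a floor at week 24, they leave a week-24 value admissible for week 52.

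Three stronger readings are tempting, and the documents do not support them:

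- *A reader might infer that the 12-week trial HbA1c could itself be carried to week 52, 40 weeks early.* Section 17 limits the follow-up group: "participants who consent to data linkage and who have HbA1c measurements post-trial will represent a non-random subset of those initially randomized". Someone whose last lab is the trial draw falls outside that group.
- *A reader might infer that early values will often be used, because post-trial labs are voluntary.* The documents give no frequency, and some of their content points the other way. Section 2 refers to usual care built on 3-monthly HbA1c, Section 7 requires diabetes contact with a primary care provider in the last 12 months, and Section 10 sends reminders.
- *A reader might infer that a vanished effect would look sustained.* In the illustration, 0.10-0.20% remains of 0.5%, so the result would still show 60-80% of the effect gone.

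It is also true that the direction depends on the course of the effect: if the difference grew after week 24, the pull would understate it.

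**Conclusion.** The point stands as a gap in a stated selection rule. Nothing in the documents prevents a value from around week 24 from being reported at week 52 and counted at both time points, for any participant with no closer lab by week 64. Where this happens, the 52-week arm difference moves towards the earlier one.

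The 0.10-0.20% figure is an illustration. Its inputs (the 0.5% early difference, the complete fade, and the 20-40% share, equal in both arms) are assumptions and not figures from the plan's follow-up. It is a partial bias in a secondary observational objective, for which Section 17 already gives up the balance of randomization. That caveat concerns who has a post-trial lab; it does not cover when the lab was taken. The 12-week primary outcome and its sample size are unaffected. The change is worth making, but the trial's main conclusion does not hang on it.

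**What to change.** Before the NetCare review, add a short rule to Sections 6, 10 and 14:

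- Week 52: the value nearest to week 52 within weeks 40-64, which mirrors the plan's own 12-week upper limit (52 − 12 = 40). If there is none, the outcome is missing.
- Week 24: the nearest value within a window that starts after the 12-week trial draw and ends before week 40, for example 24 ± 8 weeks (weeks 16-32). The exact limits are for the investigators to choose, provided that the two windows do not overlap.
- Each value is used for one time point only.
- The number missing at each time point is reported by arm.

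This needs no extra visits or data. For week 52 it changes nothing for a participant with a draw in weeks 40-64. The cost is that those without one become missing instead of receiving an earlier value, so the 52-week analysis will be smaller. With the example window, labs from between weeks 32 and 40 are used at neither time point.

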11. MITIGATION OF ANTICIPATED MINOR RISKS

Skin reaction to the device may occur, namely local dermatitis or allergy-type reactions (redness, itching, localized swelling, blisters, oozing). This reaction is usually due to a contact allergy to a component of the adhesive, e.g.: isobornyl acrylate. Systemic reactions have not been described with the device. If sufficiently bothersome or severe, skin reactions can be managed with topical steroid cream or ointment. We will refer participants to their usual providers for assessment. Subsequent sensor placement can be facilitated (if the participant remains willing) by placing a barrier product (i.e.: 3M Cavilon no sting barrier film, Tegaderm Advanced barrier, or hydrocolloid blister patch) prior to initiating a sensor.

12. MITIGATION STRATEGIES FOR COVID-19 RISKS

1. Study personnel interacting with participants face-to-face will complete and document the Alberta Health Services COVID-19 Assessment for Healthcare Workers and Workers in High Risk Settings daily (<https://myhealth.alberta.ca/journey/covid-19/Pages/HWAssessLanding.aspx>).
2. Both participants and research personnel will be required to wash hands with alcohol-based hand sanitizer and don masks during the interaction.
3. Participant-facing spaces will be disinfected with a hard surface cleaner with a broad-spectrum virucidal claim or a virucidal claim against coronaviruses, approved by Health Canada. Alcohol-based handwash will be available.

4. A brief screening call will take place ahead of the baseline study visit to ensure that all participants have received at least 2 doses of a Health Canada-approved vaccine against COVID-19.
5. Participants will be asked to reschedule their in-person encounters if they have any symptoms of COVID-19, or any close contact with an individual newly diagnosed with COVID-19 in the previous 10 days. Participants will have infrared surface temperature screening for fever at the beginning of the visit (screening form included under Documentation).

In Alberta, the current recommended isolation period for an individual with COVID-19 is 5 days (fully immunized) or 10 days (not fully immunized). Although our participants will all be fully immunized, out of an abundance of caution we will reschedule their visit for ≥ 10 days from symptom onset (or exposure to a COVID-19 case), as long as symptoms by then have improved and the participant is afebrile for ≥ 24 hours.

13. TREATMENT-EMERGENT ADVERSE EVENTS

Included participants belong to a population (adults with type 2 diabetes and are not on insulin) that does not typically experience hypoglycemia, and do not typically measure their glucose levels. No serious adverse events are expected. However, this protocol has several features to identify unexpected adverse events during the study.

- All emergency department visits and hospitalizations occurring from randomization to week 12 will be reviewed and adjudicated (see Appendix 5.6 for adverse event reporting forms) by study investigators. If a serious adverse event occurred because of the trial or trial intervention, study protocols will be reviewed and amended to mitigate the harm.
- We are performing in-person visits with participants to measure BP and weight. There is the possibility that we detect extremely abnormal physical parameters (e.g.: severe hypertension $\geq 180/110$ mmHg, severe hypotension SBP < 90 mmHg). A study investigator will be paged if a result this extreme is detected and the participant will be advised to attend the emergency department.
- For emotional or psychological distress disclosed during a study visit or interview, the interviewer will offer supportive listening, remind participants of their right to withdraw from the trial, offer to connect the participant with a study investigator, and refer participants back to their usual care provider.

14. STATISTICAL AND ANALYTICAL METHODS

Our sample size calculation was intended to detect an HbA1c difference of 0.5%, presuming a standard deviation of HbA1c values at 3 months of 0.78% based on a recent similar trial of capillary blood glucose monitoring. To have 80% power to detect this HbA1c difference at a type 1 error rate of 5%, we would need 40 trial-completers in each arm. Given expected loss-to-follow-up rates of 20% or more, our enrollment target will be 100 participants.

Data will be analyzed according to intention-to-treat principles. Patients will be kept in the study group to which they were randomized, and efforts will be taken to ascertain outcome events in all patients randomized. Discontinuation of study treatment (isCGM) or no-show to CDE encounters are not equivalent to withdrawal from the study, and efforts will be made to contact study participants for HbA1c measurements and patient-reported outcomes at 12 weeks regardless.

Outcomes (HbA1c and patient-reported outcomes) are continuous scores – the difference at 12 weeks from baseline will be presented using simple means and standard deviations. On change in HbA1c, our primary outcome, we will test for a difference between intervention and enhanced usual care arms using linear regression with adjustment for age and sex. Secondary outcomes and diabetes-related distress will be analyzed in similar fashion, including follow-up values for patient-reported outcomes obtained at 6 and 12 weeks. Safety outcomes are dichotomous (e.g.: ED visits), and differences between trial arms will be assessed using Fisher's exact test. The primary outcome will be considered statistically significant at $p < 0.05$. Secondary and safety outcomes are considered hypothesis-generating and will also be considered statistically significant at $p < 0.05$. No correction for multiple comparisons is planned *a priori*. If the primary outcome is statistically significant at $p < 0.05$, the Benjamini-Hochberg procedure will be performed on secondary outcomes targeting a false discover rate of 20%, if requested by reviewers.

Secondary analyses are planned, and include:

- Post-hoc analysis of outcomes in clinically relevant groups, e.g.: by sex, baseline self-management empowerment, etc., using the above methods.
- Partitioning participants into those who improved their HbA1c by 0.5% or more, and examining predictors of improvement using logistic regression with simultaneous incorporation of other explanatory variables.

For the post-trial cohort study, the relationship between outcomes (HbA1c and health care utilization) and study allocation will be examined using linear (log-transformed or untransformed) and logistic regression models with simultaneous adjustment for multiple other variables, selected using a mixed purposeful / stepwise method.

For the qualitative sub-study, semi-structured interviews will be transcribed verbatim, anonymized, and will undergo thematic analysis using constant comparative methods. Co-investigators will interview transcripts independently and meet to develop a coding manual. The qualitative research associate will then code the remaining transcripts line by line. Team members will meet periodically to review and refine codes using a constant comparison method, with further sampling guided by emerging themes until content saturation is achieved.

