10. STUDY OUTCOMES AND VARIABLES

Case report forms are provided in Appendix 5. These will be translated into electronic documents to be completed by participants via a password protected webportal (EpiCore).

Primary Outcome:

- Change in HbA1c at 12 weeks compared to baseline.

Secondary Outcomes:

- Feasibility of recruitment
 - Participant referral, screening, and randomization rates over time
 - Reasons for inclusion / exclusion of all participants referred.
- Change in scores at 6 and 12 weeks compared to baseline, on the patient-reported outcomes shown in Table 1, below.
- isCGM participants only – change in time-in-target range, coefficient of variation, and glucose management indicator at 12 weeks compared to baseline.

Table 1: Patient-Reported Outcomes

Outcome	Instrument	Number of items
Diabetes treatment satisfaction – Status score	Diabetes Treatment Satisfaction Questionnaire (DTSQs) ³⁷ (weeks 6 and 12)	8
Diabetes treatment satisfaction – Change score	Diabetes Treatment Satisfaction Questionnaire (DTSQc) (week 6 only)	
Self-management empowerment	Diabetes Empowerment Scale – Short Form (DES-SF) ³⁸ (weeks 6 and 12)	8
Diabetes-related distress	Problem Areas in Diabetes (PAID) Questionnaire ³⁹	20
Diet	UK Diabetes and Diet Questionnaire (UKDDQ) ⁴⁰ (weeks 6 and 12)	25
Physical activity	International Physical Activity Questionnaire (IPAQ) short form ^{41,42} (weeks 6 and 12)	7
Health status	Euroqol EQ-5D-5L (weeks 6 and 12)	5

* In addition to collection at baseline.

Safety outcomes at 12 weeks:

- Any adverse events (serious and non-serious) occurring from baseline to 12 weeks will be identified and tracked at the 12 week study visit by patient interview, and reviewed

by study investigators to determine whether clinically attributable to diabetes, diabetes management, or isCGM. isCGM issues (e.g.: skin reactions) will be specifically sought.

- Emergency department visits or hospital admission for any reason, identified from patient interview and from NetCare review.

Qualitative Outcomes: Semi-structured interviews will undergo thematic analysis using constant comparative methods. The starting point will be the participant and provider experience with isCGM or enhanced usual care, with a particular focus on barriers and enablers of effectiveness (see Appendix 6, interview guides). Semi-structured interviews will take place for participants after trial completion (from 12-24 weeks).

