Appendix 5.5: HbA1c and Time in Range Form

HbA1c Report Form

Research assistant to complete

Patient study ID

Follow-up time: Baseline, 12 weeks

HbA1c value

Date of HbA1c

isCGM Time-in-Range Report Form

Research assistant to complete

Patient study ID

Follow-up time: 12 weeks

For adults randomized to the isCGM group only

Date of first sensor start:

Date of second sensor start:

Date of third sensor start:

Referring to the first two weeks of isCGM sensor use:

- Start date:
- Time-in-range (3.9-10.0 mmol/L) (%):
- Time-above-range (>10.0 mmol/L and <= 13.9 mmol/L):
- Time-above-range – severe (> 13.9 mmol/L):
- Time-below range (sum of < 3.9 mmol/L and < 3.0 mmol/L):
- Glucose Management Indicator (GMI) (%):
- Coefficient of variation (CV):

Referring to the last two weeks of isCGM sensor use:

- Start date:
- Time-in-range (3.9-10.0 mmol/L) (%):
- Time-above-range (>10.0 mmol/L and <= 13.9 mmol/L):
- Time-above-range – severe (> 13.9 mmol/L):
- Time-below range (sum of < 3.9 mmol/L and < 3.0 mmol/L):
- Glucose Management Indicator (GMI) (%):
- Coefficient of variation (CV):

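### The primary model leaves out baseline HbA1c, which is collected, and the 80% power was worked out for 3-month values, not for the change that is tested

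*Combined protocol and SAP*

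**What the plan says.** Section 10 defines the primary outcome as "Change in HbA1c at 12 weeks compared to baseline". Section 14 gives the test: "we will test for a difference between intervention and enhanced usual care arms using linear regression with adjustment for age and sex". No other covariate is named for it. The wider adjustment described later in Section 14 belongs to the responder analysis and the post-trial cohort, not to the primary comparison.

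Baseline HbA1c is available. The HbA1c report form in Appendix 5.5 carries "Follow-up time: Baseline, 12 weeks", and the honorarium in Section 8 depends on receipt of both values.

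The sample size in Section 14 is for a difference of 0.5%, "presuming a standard deviation of HbA1c values at 3 months of 0.78"%, with 80% power and a 5% type 1 error rate, giving 40 completers per arm. The synopsis repeats it: "The minimum number of trial completers required to have 80% power to detect an HbA1c difference of 0.5% is 80". Section 17 states "Our study is powered to detect a 0.5% difference in HbA1c at a power of 80"%. The synopsis also gives "expected loss to follow-up of 20-30"%, with 100 to be enrolled.

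For the other continuous outcomes, Section 14 says "Secondary outcomes and diabetes-related distress will be analyzed in similar fashion".

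**The concern.** There are two linked points.

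1. **Precision.** Baseline HbA1c is the most obvious predictor of 12-week HbA1c. Subtracting it fixes its slope at 1. Including it as a covariate lets the data estimate the slope and, in large samples, is at least as precise. The plan adjusts for age and sex but not for this.
2. **Power.** The SD used is that of follow-up values, while the test is on change. The two SDs can differ in either direction, depending on the correlation and the baseline SD, and the plan states neither.

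This is the trial's only confirmatory test. At stake are a possibly large but avoidable loss of precision and a power statement, made in the synopsis, Section 14 and Section 17, that has no stated basis for the planned analysis.

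**Working it through.** **Inputs.** From Section 14: difference 0.5%, SD of 3-month values 0.78%, type 1 error 5%, 40 completers per arm. From the synopsis: 1:1 allocation and loss of 20-30% of 100 enrolled, so 30% loss leaves 70 completers, or 35 per arm. Sidedness is not stated. Two-sided is assumed because it reproduces 40 per arm, whereas one-sided gives 31.

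Not in the documents, so taken over a range: the correlation ρ between baseline and 12-week HbA1c, and k = baseline SD / follow-up SD.

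**The plan's own figure.** For a two-sample comparison of 3-month values, the noncentrality is 0.5 / (0.78 × √(2/40)) = 2.87. Noncentral-t power is 80.8% at 40 per arm and 79.8% at 39. The 40 per arm is correct for that comparison.

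**The SD each model faces.**
- Change, without baseline: 0.78 × √(1 + k² − 2ρk)
- With baseline as covariate: 0.78 × √(1 − ρ²)

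The first variance minus the second is 0.78² × (k − ρ)². It is never negative and is zero only when ρ = k, that is, when the slope of 12-week on baseline HbA1c (ρ/k) is 1. The second SD can never exceed 0.78.

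**Power with k = 1.** The first figure is the noncentral-t formula, with 2n − 4 and 2n − 5 degrees of freedom for n per arm. The second is a simulation of 100,000 trials per cell, with age and sex as noise covariates.

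| ρ | SD of change | SD with baseline | 40/arm, planned | 40/arm, with baseline | 35/arm, planned | 35/arm, with baseline |
|---|---|---|---|---|---|---|
| 0 (lower bound) | 1.10 | 0.78 | 51.7 / 50.5% | 80.8 / 79.1% | 46.4 / 45.5% | 75.2 / 73.2% |
| 0.3 | 0.92 | 0.74 | 66.7 / 65.7% | 84.3 / 83.0% | 60.8 / 59.5% | 79.1 / 77.2% |
| 0.5 | 0.78 | 0.68 | 80.8 / 79.5% | 90.5 / 89.2% | 75.3 / 74.2% | 86.2 / 84.8% |
| 0.7 | 0.60 | 0.56 | 95.5 / 94.9% | 97.7 / 97.3% | 92.7 / 91.9% | 95.9 / 95.2% |

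The simulation runs up to about 2 points lower because it includes chance covariate imbalance. Mean 95% CI width at 40 per arm, planned against with baseline, is 0.830 against 0.674 at ρ = 0.3, 0.702 against 0.612 at 0.5, and 0.543 against 0.504 at 0.7.

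**When the planned test reaches 80%.** The largest SD of change that gives 80% power is 0.788 at 40 per arm and 0.736 at 35. Solving ρ = (1 + k² − (SDmax/0.78)²) / (2k):
- 40 per arm: ρ of about 0.39, 0.49, 0.59 and 0.74 for k = 0.8, 1, 1.2 and 1.5
- 35 per arm: ρ of about 0.56 for k = 1

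These are formula values. The simulated 79.5% at ρ = 0.5 shows that the true thresholds are slightly higher.

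**Near slope 1.** At ρ = 0.75 and k = 0.8 the slope is 0.75 / 0.8 = 0.94. With 40 per arm, mean CI width is 0.465 planned against 0.467 with baseline, and power is 98.8% against 98.7%. There is no gain and almost no loss.

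**Validity.** Under the null at ρ = 0.5, simulated type 1 error is 5.0% planned and 5.1% with baseline (40 per arm), and 5.0% for both at 35 per arm. Mean estimates are within 0.001 of zero for both models.

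**The case against.** The planned analysis is valid, and 40 per arm contains no arithmetic error. The 0.78% comes from an outside trial that the reader cannot check. If it was really an SD of change, the 80% stands for the planned test. A correlation of 0 is implausible: Section 17 itself says that the 12-week HbA1c may reflect glucose exposure early in the trial, which points to a positive correlation. At ρ = 0.7 the gain is only about 2 points, and near slope 1 it is nil. Loss of 30% reduces power whatever the covariates.

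Much of this stands. The test is not biased, underpowering is not shown, the size of the gain is unknown, and the ρ = 0 row is a bound, not an expected case. The loss question is separate, although it narrows the margin.

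It does not remove the point. Section 14 calls 0.78% the SD of values at 3 months. If it was an SD of change (k = 1), the residual SD with baseline would be 0.78 × √((1 + ρ)/2). That is 0.63 at ρ = 0.3 and 0.74 at ρ = 0.8, and power at 40 per arm would still rise from about 81% to between 94% and 85%. On either reading, adding baseline costs almost nothing where it does not help and gains materially where it does.

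**Conclusion.** The point holds, as a recommended low-cost improvement rather than a flaw that invalidates the trial. Baseline HbA1c is collected and omitted from the primary model, and the 80% power is not established for a test on change.

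Over correlations of 0.3 to 0.7, with equal SDs and 40 completers per arm, the formula power of the planned test runs from 67% to about 95%. With baseline added it runs from 84% to 98%. Without baseline, 80% needs a correlation of about 0.5 if the SDs are equal, and a higher one if the baseline SD is larger. With baseline, the plan's input supports about 80% or more at any non-negative correlation (79% simulated and 81% by formula at zero).

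These figures assume a two-sided 5% test, a follow-up SD of 0.78% and a true difference of 0.5%. The correlation and SD ratio are assumptions.

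**What to change.** **Primary model (Section 14).** Add baseline HbA1c as a prespecified covariate alongside age and sex. The outcome may be change or the 12-week value, because the arm coefficient is the same. Do this before any outcome data are examined, since Section 6 says that the analysts are not blinded.

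**Sample-size paragraph.** Confirm against the source that 0.78% is the SD of follow-up values, and say so. State that with 40 completers per arm the baseline-adjusted analysis has about 80% power or more for any correlation of 0 or higher. State also that with 30% loss (35 per arm) power is about 73-75% at a correlation of 0, 77-79% at 0.3 and 85-86% at 0.5.

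**Continuous secondary outcomes.** Add the baseline value where one is collected: DTSQs, DES-SF, PAID, UKDDQ, IPAQ, EQ-5D-5L, blood pressure and weight. The DTSQc has no baseline score and is exempt. Waist circumference has no field on the baseline form (Appendix 5.2), so it qualifies only if a baseline value is recorded. The follow-up form (Appendix 5.3) lists no blood pressure, weight or waist field, so check where those 12-week values are entered.

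**Cost.** A line on the model, a few sentences on sample size, and one degree of freedom. No new data and no change in enrolment.
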